2.2 Design Summary

This will be a non-randomized, multicenter, prospective study conducted at up to forty-five (45) Clinical Investigative Sites (referred to as "Sites" in the remainder of this document), with up to 40 sites in the U.S and up to 5 sites in Japan with the objective of determining whether the TBE device is safe and effective in treating lesions of the aortic arch and descending thoracic aorta. A minimum of 175 and up to a total of 465 Subjects will be enrolled across four independent study arms consisting of seven cohorts as described below. The anatomically suitable non-aneurysm cohorts will be referred to as the Non-Aneurysm Lesion (NAL) Cohorts.

The study will consist of seven cohorts described as follows:

- Zone 2, aneurysm patients (N=115, maximum)
 - Zone 2, aneurysm patients, Primary Enrollment (N=85)
 - Zone 2, aneurysm patients, Continued Access Enrollment (N=30, maximum)
- Zone 2, anatomically suitable non-aneurysm patients, descriptive analysis (N=200, maximum)
 - Dissection cohort (N=20 minimum)
 - Traumatic Transection cohort (N=10 minimum)
 - Other isolated lesion types cohort (No minimum)
- Zone 0/1, aneurysm patients, hypothesis driven (N=50, 0-10 Subjects from Japan) NOTE: due to removal of the 49/53mm device sizes from this trial, any Subjects enrolled with these device sizes will not be counted as part of this N=50 enrollment and replacement Subjects will be enrolled to keep N=50)
- Zone 0/1, anatomically suitable non-aneurysm patients, descriptive analysis (N=100, maximum)

CONFIDENTIAL INFORMATION

- Dissection cohort (N=10 minimum)
- Other isolated lesion types cohort (No minimum)

The Zone 2 aneurysm cohort will consist of 85 subjects accrued during the Primary Enrollment period along with a maximum of 30 subjects accrued during the Continued Access Enrollment period. Any Zone 2 training cases enrolled from Japan would not be included in PMA analysis, nor do they count towards enrollment minimums/maximums as shown above. However, once enrolled, the Japan Zone 2 training cases may be included for some analysis.

The maximum number of Subjects that may be enrolled at a single site is as follows:

- Zone 2, aneurysm patients, 17 Subjects
- Zone 0/1, aneurysm patients, 8 Subjects in US, 4 Subjects in Japan
- Zone 2 and Zone 0/1, anatomically suitable non-aneurysm patients, all cohorts, will not have a maximum per site as they are for descriptive analysis only

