2.3.1.1 Zone 2 Aneurysm Cohort

The Primary Endpoint for the Zone 2 aneurysm cohort will be a composite of the following events through 12 months (through day 546 unless otherwise specified in study protocol component definitions) following the index endovascular procedure:

- Device Technical Success
- Absence of the following:
 - Aortic rupture;
 - Lesion-related mortality;
 - Disabling stroke
 - Permanent paraplegia
 - Permanent paraparesis
 - New onset renal failure requiring permanent dialysis
 - Additional unanticipated post-procedural surgical or interventional procedure related to the device, procedure, or withdrawal of the delivery system.
- 2.3.1.2 Zone 0/1 Aneurysm Cohort

[figure not shown]
The Primary Endpoint for the Zone 0/1 aneurysm cohort will be Strategy Success.

Strategy Success (For planned staged procedures – landing zone optimization, transposition, and device placement – through one month following last planned procedure) and is defined as follows: a composite of the following events from the time of enrollment through one month following the index endovascular procedure (through day 59 unless otherwise specified in study protocol component definitions):

[figure not shown]
- Initiation of the index endovascular procedure following the debranching procedure
- Device technical success for the index endovascular procedure
- Absence of the following :
 - Aortic rupture
 - Lesion-related mortality
 - o Disabling Stroke
 - Permanent paraplegia
 - Permanent paraparesis
 - New onset renal failure requiring permanent dialysis

GORE CONFIDENTIAL INFORMATION

 Additional unanticipated post-procedural surgical or interventional procedure related to the device, procedure, or withdrawal of the delivery system.

GORE CONFIDENTIAL INFORMATION

2.4 **Statistical Hypotheses**

- 2.4.1 Performance Goal Derivation
 - 2.4.1.1 Zone 2 Aneurysm Cohort

Historical TAG/CTAG results (TAG 99-01, TAG 03-03, TAG 04-02, TAG 05-02, TAG 08-03) were re-analyzed to determine the Zone 2 aneurysm cohort performance goal for the Primary Endpoint (see study protocol for this data). Subjects treated for DTA aneurysms with proximal device placement in Zone 2

GORE CONFIDENTIAL INFORMATION

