5.1 Analysis Populations

- 5.1.1 Primary Endpoint
 - 5.1.1.1 Zone 2 Aneurysm Cohort

The composite Primary Endpoint analysis population (to test the hypothesis) for the Zone 2 aneurysm cohort will be among enrolled Subjects (excluding those with a CEC adjudicated 'major' inclusion/exclusion criteria violation or FDA mandated exclusion) and is outlined as follows based on events described in **Section 2.3.1.1**:

- 1) Subjects with an event any time ≤ 546 days are a failure regardless of whether they had imaging in 12 month window
- Subjects that don't have imaging in the 12 month window and don't have an event ≤ 546 days are excluded
- Subjects with imaging in 12 month window and no event reported ≤ 546 days are successes
- 4) Subjects with >1 event just count once as failures

The rate (composite Primary Endpoint) within an analysis window (except for Procedure window) will use similar logic to that through 12 month window but will be window-dependent (i.e. 6 Month Primary Endpoint composite rate will be among those with an event in the 6 month window or had imaging in the 6 month window). All enrolled Subjects with no 'major' inclusion/exclusion criteria will be in the denominator in the Procedure window.

GORE CONFIDENTIAL INFORMATION

All hypothesis testing and Primary Analysis for the PMA will be based on Zone 2 Aneurysm Subjects accrued during the Primary Enrollment Period. Zone 2 Aneurysm Subjects accrued during Continued Access Enrollment will be analyzed separately for the PMA. Continued Access Enrollment Subjects may be pooled with the Primary Enrollment Subjects in subsequent reports and/or analysis.

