5.3 Primary Endpoint Analysis

5.3.1 Zone 2 and Zone 0/1 Aneurysm Cohorts

The proportion of composite Primary Endpoint success (1 - composite Primary Endpoint failure) will be calculated for each hypothesis-driven cohort based on the details outlined for each Primary Endpoint component in **Appendix A**. One-sided Exact confidence intervals for binomial proportions (alpha=0.05) will be constructed to test each calculated composite proportion against the respective Primary Endpoint hypothesis. Each hypothesis-driven cohort tested must meet their respective Primary Endpoint analysis population criteria. The null hypothesis will be rejected if the lower bound of the 95% confidence interval estimating composite Primary Endpoint success exceeds the performance goal.

In addition, the Primary Endpoint data (composite and components) for each of these two cohorts will be summarized by statistics (count and percent).

In order to assess the impact of missing data on each of the composite Primary Endpoint hypothesis tests, sensitivity analyses will be performed and are outlined in **Section 5.5.1**.

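### The within-window composite in SAP 5.1.1.1 lets a subject who has already failed count as event-free in a later window, so it is neither an at-risk interval rate nor a cumulative success rate

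*SAP*

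**What the plan says.** SAP 5.1.1.1 gives two rules for the Zone 2 aneurysm composite.

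- **Tested endpoint.** This rule is cumulative: "Subjects with an event any time ≤ 546 days are a failure regardless of whether they had imaging in 12 month window". Its counterpart is "Subjects with imaging in 12 month window and no event reported ≤ 546 days are successes".
- **Rate within a window.** For every window except Procedure, the rate "will use similar logic to that through 12 month window but will be window-dependent". The SAP's example is that the "6 Month Primary Endpoint composite rate will be among those with an event in the 6 month window or had imaging" in that same window.

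The components in SAP 2.3.1.1 include disabling stroke, "Permanent paraplegia", permanent paraparesis, permanent dialysis and Device Technical Success. Appendix A determines the last of these from the index-procedure form.

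Analysis windows run to 60 months (SAP 4.3, Table 3). For Zone 2, the readable text states a cumulative composite only through 12 months. SAP 5.1.1.3 carries similar logic over to the non-aneurysm cohorts.

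**The concern.** Put a window in place of the 546-day limit and the success rule becomes: imaged in this window, no event in this window. A subject who failed earlier and has no new event can then be treated in only two ways. If not imaged, the subject leaves the denominator. If imaged, the subject enters on the success side. Neither route records the failure.

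Several components do not reverse, and a technical failure at the index procedure cannot recur. Such a subject would move from failure to event-free within the same composite.

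What is at stake is how the descriptive results are read. A figure called a 6-month Primary Endpoint composite rate invites the reading that this share of the cohort was free of failure at 6 months. In the windows from 24 to 60 months, the window rule is the only readable Zone 2 composite rule, so no cumulative figure is specified to stand beside it. The non-aneurysm cohorts are summarised by count and percent only (SAP 5.3.2), with no hypothesis test to anchor interpretation.

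**Working it through.** The documents state no within-window rate, so there is no figure to reproduce. The check is to write the competing rates in common terms and count.

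**Notation for one window**

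- S: imaged in the window, never failed
- L: first failure in the window
- Ei: failed earlier, imaged in the window, no new event
- Er: failed earlier, new event in the window
- En: failed earlier, neither imaged nor with a new event (including deaths)

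**Formulas**

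- As written: (S + Ei) / (S + Ei + L + Er)
- Earlier failures removed: S / (S + L)
- Cumulative through the window: S / (S + L + Ei + Er + En)

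**Direction.** The as-written rate has a numerator at least as large as the cumulative rate's and a denominator no larger. It can never fall below cumulative success. Against the at-risk rate the direction is not fixed, because new events in earlier failures (Er) can pull it down.

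**Illustration 1: 6-month window, days 60–242**

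From the documents: N = 85 (SAP 2.2) and the window limits (SAP 4.3, Table 3). Assumed: 12 fail by day 59, of whom 9 are alive and imaged later without a new event and 3 have died; 2 first failures occur in days 60–242; all other survivors are imaged. So S = 85 − 12 − 2 = 71, L = 2, Ei = 9, Er = 0, En = 3.

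| Rate | Count | Result |
|---|---|---|
| As written | (71 + 9)/(71 + 9 + 2) = 80/82 | 97.56% |
| Earlier failures removed | 71/(71 + 2) = 71/73 | 97.26% |
| Cumulative through 6 months | 71/(71 + 2 + 9 + 0 + 3) = 71/85 | 83.53% |

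The gap from as written to cumulative is 97.56 − 83.53 = 14.03 points. Keeping earlier failures in the denominator accounts for 97.56 − 97.26 = 0.30 points. The other 97.26 − 83.53 = 13.73 points are the difference between an interval and a cumulative quantity.

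**Illustration 2: 12-month window, days 243–546**

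The historical 81% success (SAP 2.4.1.1) is used only for scale: 0.81 × 85 = 68.85, taken as 69 successes and 16 failures. The number failing before day 243 is varied, with all of them imaged in the window and no repeat events.

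| Early failures | As written | Earlier failures removed | Cumulative |
|---|---|---|---|
| 0 | 69/85 = 81.2% | 69/85 = 81.2% | 69/85 = 81.2% |
| 4 | 73/85 = 85.9% | 69/81 = 85.2% | 81.2% |
| 8 | 77/85 = 90.6% | 69/77 = 89.6% | 81.2% |
| 12 | 81/85 = 95.3% | 69/73 = 94.5% | 81.2% |
| 16 | 85/85 = 100% | 69/69 = 100% | 81.2% |

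In these cases the as-written rate exceeds the at-risk rate by 1 point or less, and exceeds the cumulative rate by 0 to 18.8 points.

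**Scale from the SAP's own estimate.** SAP 2.4.1.1 puts technical-success events at the procedure at 5–7%, read here as an event rate. That is 0.05 × 85 = 4.25 to 0.07 × 85 = 5.95, or about 4 to 6 subjects who cannot fail again on that component.

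**The case against.** The strongest reply is that the plan knowingly names two quantities, a rate within a window and a rate through 12 months. Summaries by window are its convention elsewhere: adverse events (SAP 5.5.4), Core Lab findings (5.5.5) and reinterventions (5.5.7). A subject with an earlier stroke can still have a rupture or reintervention, so keeping that subject in a new-event denominator is coherent. Earlier deaths leave the denominator of any interval rate. The SAP also states the denominator but not the numerator, so counting an earlier failure as event-free is inferred from its reference to similar logic.

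Much of this stands. A new-event rate per window is a legitimate summary if it is labelled as one, and the loss of earlier deaths is not a fault in itself. What remains is that a composite carrying the Primary Endpoint name mixes subjects still at risk of a first failure with subjects who have already failed, and the readable text does not say so.

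A reader might infer three stronger things that the documents do not support:

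- **That the hypothesis tests are inflated.** They are not. SAP 5.1.1.1 counts any event up to day 546 and 5.1.1.2 any event up to day 59, and SAP 5.3.1 tests those composites. The repeat Zone 0/1 analysis at 12 months follows the cumulative logic too.
- **That the whole 14-point gap comes from keeping earlier failures.** In the first illustration that accounts for 0.3 points.
- **That the published table will show rising success.** No table layout is readable, the documents give no event timing, and parts of the SAP are withheld and could hold a further rule.

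**Conclusion.** The point holds for the descriptive within-window composite only. As written, and on the natural reading, an earlier failure imaged later without a new event is counted as event-free. The resulting rate cannot be lower than cumulative success and should not be presented as Primary Endpoint success at that time.

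The size is illustrative: 97.6% as written, 97.3% with earlier failures removed and 83.5% cumulative through 6 months. It rests on the assumed split of 12 early failures (9 imaged, 3 dead) and 2 later ones, and on complete imaging of the other survivors. The ordering of the as-written and cumulative rates does not depend on those assumptions, but the distance between them does. Since nearly all of that distance is interval versus cumulative, the practical gain comes from adding the cumulative row. Removing earlier failures makes the window row interpretable but barely moves it. Alpha, power and the decisions against 64% and 60% do not change.

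**What to change.** In SAP 5.1.1.1, and by reference for the non-aneurysm cohorts in 5.1.1.3:

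1. For each window after the procedure, report a cumulative composite through the window end. A subject fails if any component occurred on or before that day.
2. If the window row is kept, remove from its denominator every subject who failed in an earlier window. Label it 'first failure in this window', not Primary Endpoint success.
3. State that each event is assigned to the window of its onset, so that programmers do not have to decide.

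The cost is a few sentences of SAP wording and one re-programmed table. No new data are needed. The descriptive figures will look less favourable, almost entirely because of the cumulative row.

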5.1.1.2 Zone 0/1 Aneurysm Cohort

The composite Primary Endpoint analysis population (to test the hypothesis) for the Zone 0/1 aneurysm cohort will be among enrolled Subjects (excluding those with a CEC adjudicated 'major' inclusion/exclusion criteria violation or FDA mandated exclusion) and is outlined as follows based on events as described in Section 2.3.1.2:

- Subjects with an event any time \leq 59 days are a failure regardless of whether they had imaging in one month window
- Subjects that don't have imaging in the one month window and don't have an event \leq 59 days are excluded
- Subjects with imaging in one month window and no event reported \leq 59 days are successes
- Subjects with >1 event just count once as failures

The analysis population for the Zone 0/1 Aneurysm cohort will also exclude any Subjects treated with a 49/53mm device since those device sizes have been removed from this study. Any Subjects enrolled and treated with those device sizes will not be counted in the N=50 enrollment and replacement Subjects will be enrolled to keep N=50. The 49/53mm Subjects will be summarized separately and followed per the Protocol.

This analysis will also be repeated with 12 month results (following the same analysis population logic as that outlined for the Zone 2 aneurysm cohort in Section 5.1.1.1) with the exception that no hypothesis will be tested.

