	
 ○ Disabling stroke; ○ Permanent paraplegia; ○ Permanent paraparesis; ○ New onset renal failure requiring permanent dialysis; ○ Additional unanticipated post-procedural surgical or interventional procedure related to the device, procedure, or withdrawal of the delivery system. 
Primary Endpoint- Zone 0/1 Subjects (Aneurysm Cohort) Composite of the following events from time of enrollment through one month following endovascular procedure:
 
 ● Initiation of the index endovascular procedure following the debranching procedure ● Device Technical Success for the index endovascular procedure ● Absence of the following: 
 ○ Aortic rupture; ○ Lesion-related mortality; ○ Disabling stroke; ○ Permanent paraplegia; ○ Permanent paraparesis; ○ New onset renal failure requiring permanent dialysis; ○ Additional unanticipated post-procedural surgical or interventional procedure related to the device, procedure, or withdrawal of the delivery system.
Subject Population	Subjects with thoracic aortic lesions which require coverage of the left subclavian artery, left common carotid artery and/or the brachiocephalic trunk/innominate artery for effective treatment.
Number of Subjects	
Total Enrollment of 175-465 Subjects across four independent arms with a total of seven cohorts as follows:
 
 ● Zone 2 – Aortic Aneurysm; A maximum of 115 Subjects 
 ○ Primary Enrollment (n=85 Subjects) ○ Continued Access Enrollment (maximum 30 Subjects) ● Zone 2 – Non-aneurysm aortic lesions; A maximum of 200 Subjects in all cohorts combined. 
 ○ Dissection cohort (minimum 20 Subjects) ○ Traumatic Transection cohort (minimum 10 Subjects) ○ Other isolated lesion types

	
 • Zone 0/1 – Aortic Aneurysm; 50 Subjects • Zone 0/1 – Non-aneurysm aortic lesions; A maximum of 100 Subjects in all cohorts combined. 
 ○ Dissection cohort (minimum 10 Subjects) ○ Other isolated lesion types
Number of Sites	Up to 40 sites in the U.S. (Zone 2 and Zone 0/1) and up to 5 sites in Japan (Zone 0/1).
Coordination PI	

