2.4.1.2 Zone 0/1 Aneurysm Cohort

A systematic literature review of hybrid repair literature was conducted (see study protocol for in-depth description of this literature review). Key results that were consistently identifiable from the review included perioperative death, neurological events and spinal cord ischemia, all of which are part of the Zone 0/1 Primary Endpoint. The results were individually summarized (i.e., a rate for each outcome was calculated across the identified literature) and then summed up; the estimated total percent of these events was 23.6%. Additional events included in the Primary Endpoint of the Zone 0/1 statistical arm are renal failure and the components of technical success. To account for these additional factors, an adjustment of 11% to the overall point estimate from the literature analysis was employed, increasing the anticipated point estimate from historical results to 34.6%. To account for potential variability in the new study population an additional margin of 5% was incorporated. This additional adjustment to the performance goal is justified given the potential for underreporting of key events in literature and national databases. Due to this consideration, the study performance goal (success) for the proposed Zone 0/1 Primary Endpoint was set at 60%.

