4.3 Follow-Up Visit Windows

Follow-up visits will be scheduled at appointed times after the date of treatment. Follow-up visits should be scheduled within the ideal window when possible; however, any available data collected in the analysis windows will be summarized as occurring within the given window. Thus, a period during which each visit is allowed, i.e. window, is provided in **Table 3** (Zone 2) and **Table 4** (Zone 0/1).

Follow-up Visit	Ideal Window (days)	Analysis Window (days)	Adverse Event Absolute Analysis Window (days)
Procedure	0	0	0
Post-Procedure	1-14	1-14	-
1 Month	23-44	15-59	1-30
6 Months	150-210	60-242	31-182
12 Months	275-455	243-546	183-365
24 Months	640-820	547-911	366-731
36 Months	1005-1185	912-1275	732-1096
48 Months	1370-1550	1276-1640	1097-1461
60 Months	1735-1915	1641-2006	1462-1826

Table 3: Zone 2 Cohorts Schedule of Follow-up Visits and Time Periods

		· ·	
Follow-up Visit	Ideal Window (days)	Analysis Window (days)	Adverse Event Absolute Analysis Window (days)
Phase 1 Procedure:	-7 up to -1 days before	-60 up to -1 days	-60 up to -1 days
Great Vessel	Phase 2 Procedure	before Phase 2	before Phase 2
Revascularization		Procedure	Procedure
Phase 1 Evaluation	-6 up to 0 days before Phase	-59 up to 0 days	-59 up to 0 days
	2 Procedure*	before Phase 2	before Phase 2
		Procedure*	Procedure*
Phase 2 Procedure:	0	0	0
Index Endovascular			
Procedure			
Post Procedure	1-14	1-14	-
1 Month	23-44	15-59	1-30
6 Months	150-210	60-242	31-182
12 Months	275-455	243-546	183-365
24 Months	640-820	547-911	366-731
36 Months	1005-1185	912-1275	732-1096
48 Months	1370-1550	1276-1640	1097-1461
60 Months	1735-1915	1641-2006	1462-1826

Table 4: Zone 0/1 Cohorts Schedule of Follow-up Visits and Time Periods

* Although Phase 1 Evaluation can occur on the same day as the Index Endovascular Procedure, the Phase 1 Evaluation must occur before the Index Endovascular Procedure

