5.2.2 Zone 0/1 Aneurysm Cohort

The Primary Endpoint for the Zone 0/1 aneurysm cohort will be analyzed after all available Subjects meeting the analysis population criteria have completed the one month follow-up visit and have been in the study through 59 days. Subjects with suspected stroke Primary Endpoint events will need to have been in the study through 120 days before this Primary Endpoint analysis will be performed. This extra time is needed for these Subjects to allow for the Modified Rankin Scale to be assessed at any time during this period.

This analysis will also be repeated with 12 month results (following the same analysis population logic as that outlined for the Zone 2 aneurysm cohort in **Section 5.1.1.1**) with the exception that no hypothesis will be tested.

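### In Zone 0/1, an event-free subject who leaves the study after an early one-month scan still counts as a success through day 59

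*SAP*

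**What the plan says.** The Protocol summary defines the Zone 0/1 primary endpoint as a "Composite of the following events from time of enrollment through one month following endovascular procedure". SAP 2.3.1.2 uses the same period in words and adds a day limit: "through day 59 unless otherwise specified in study protocol component definitions".

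SAP 5.1.1.2 then sorts subjects as follows:
- Subjects with an event by day 59 "are a failure regardless of whether they had imaging in one month window".
- Event-free subjects with no scan in the one-month window are excluded.
- "Subjects with imaging in one month window and no event reported" to day 59 are successes.

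Table 4 in SAP 4.3 gives three one-month windows: ideal days 23-44, analysis days 15-59 and adverse events days 1-30. The analysis window governs, because "any available data collected in the analysis windows will be summarized as occurring within the given window".

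SAP 5.2.2 delays the primary analysis until all available subjects "have completed the one month follow-up visit and have been in the study through 59 days", or through day 120 for a suspected stroke.

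**The concern.** The failure rule and the success rule rest on different amounts of observation. A failure can be recorded on any day to 59. A success needs one scan, possibly on day 15, and the absence of a report afterwards. For a subject who stays in the study, absence of a report is informative, because adverse events are collected until study completion or discontinuation (SAP 5.5.4.1.3). For a subject who leaves after the scan it is not, yet 5.1.1.2 credits that subject with the whole period. The wait in 5.2.2 covers subjects who are still available and does not reclassify one who has gone.

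The error can run only in the device's favor. With 50 subjects each one is worth 2 percentage points, so the classification should be settled before the result is known.

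**Working it through.** **Inputs.** Goal 60% (SAP 2.4.1.2 and 2.4.3); n = 50 with no attrition allowed for (SAP 2.4.3 as printed); exact one-sided test at alpha 0.05 (SAP 5.3.1); windows from Table 4.

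**The plan's own figure.** The SAP says a point estimate above 74% is needed. The rule is to pass if P(X ≥ x | n = 50, p = 0.60) ≤ 0.05, which is the same as an exact lower bound above 60%.

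| Successes | Rate | One-sided p | Lower bound | Result |
|---|---|---|---|---|
| 36/50 | 72% | 0.0540 | 59.7% | fail |
| 37/50 | 74% | 0.0280 | 61.9% | pass |
| 38/50 | 76% | 0.0133 | 64.0% | pass |

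The stated threshold is reproduced to within one subject: 74% exactly is already enough under 5.3.1.

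**Time not covered after the scan.** With a scan on day 15, 59 − 15 = 44 days (44/59 = 75%). Within the ideal window, a day-23 scan leaves 36 days (61%) and a day-44 scan leaves 15 days (25%). These days are unobserved only if the subject leaves.

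**Expected size.** The documents give no exit or late-event rates, so these are assumptions. Let f be the share leaving after a qualifying scan (2% to 20%) and h the event risk over days 15-59 (2% to 5%). As a worst case, all of that risk goes unseen.
- Hidden failures = 50 × f × h: from 50 × 0.02 × 0.02 = 0.02 to 50 × 0.20 × 0.05 = 0.5 subject.
- If true day-59 success is 60%, the credited rate is 0.60 + f × h, from 0.6004 to 0.61. P(X ≥ 37) rises from 0.0280 to between 0.0284 and 0.0384, still below 0.05.

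**Effect at the margin.** Suppose the result is exactly 37/50 and k of the successes left early.

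| k | Counted as failures | Excluded |
|---|---|---|
| 1 | 36/50, bound 59.7%, fail | 36/49, bound 61.2%, pass |
| 2 | 35/50, bound 57.6%, fail | 35/48, bound 60.4%, pass |
| 3 | 34/50, bound 55.5%, fail | 34/47, bound 59.7%, fail |

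At 40/50, four such subjects would have to be counted as failures to lose the result (36/50). The handling rule therefore matters only near the threshold, but there it decides.

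**Direction of the day-59 cut-off.** Assume 80% success at day 30, which gives power 0.889 at 37/50. If a further 1, 2, 3 or 5 points fail on days 31-59, power is 0.851, 0.806, 0.754 or 0.637. Counting failures to day 59 works against the device; only the credit for early leavers works for it.

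**The SAP's other 30-day limits.** The adverse-event window for the visit ends at day 30. The extra Modified Rankin assessment (Table 2 footnote) is triggered only by a suspected stroke within 30 days and must be done by day 120. A stroke on days 31-59 would reach 90 days on days 121-149 (31 + 90 and 59 + 90), past that limit and past the day-120 wait in 5.2.2. Unless unseen component definitions deal with this, these passages need to be reconciled.

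**The case against.** **A reader might infer that the SAP departs from the Protocol.** The documents do not show that. Both give the same period in words. The public Protocol is a summary without day windows, and the SAP defers to Protocol component definitions that are not public. Day 59 is simply the upper edge of the SAP's one-month analysis window, used as day 546 is for Zone 2.

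**A reader might also infer a proven mismatch with the benchmark**, because "Key results that were consistently identifiable from the review included perioperative death, neurological events and spinal cord ischemia". SAP 2.4.1.2 gives no time window for those rates, and the word perioperative stands only before death. The literature review is in Protocol text that is not public. The goal also contains allowances: "an adjustment of 11% to the overall point estimate from the literature analysis was employed", then 5 points for variability, justified by possible underreporting (23.6 + 11 + 5 = 39.6% failure, so 60.4% success, set at 60%). Even if late events are missing from the benchmark, counting them in the trial is conservative.

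**The early-exit case is rare.** It needs a scan followed by departure before day 59. That is correct and is why the expected effect is small.

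**It may already be covered.** SAP 5.3.1 promises missing-data sensitivity analyses in 5.5.1, and SAP 4.0 refers to lost-to-follow-up rules in the Protocol. Neither text is public, so this cannot be excluded. However, under 5.1.1.2 as written such a subject is classified as a success, so is not missing on its face.

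**Requiring contact at day 59 could burden compliant subjects**, since the ideal visit window closes on day 44. In practice the 6-month visit documents status past day 59 for most subjects, given planned accrual of 48-60 months.

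**Conclusion.** The gap is real and narrow. As written, SAP 5.1.1.2 counts an event-free subject who leaves between the scan and day 59 as a success for time nobody observed. It does not affect subjects who remain in follow-up. On the assumed exit and event rates the expected effect is under one subject, and type I error is at most 0.0384. It could change the decision only for a result at or near 37/50, where one reclassified subject gives 36/50 and a failed test. No departure from the Protocol and no proven benchmark mismatch are established. This is a low-priority clarification, and unseen text in SAP 5.5.1 or the full Protocol may already supply part of it.

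**What to change.** 1. In SAP 5.1.1.2, require two things for success: imaging in the one-month window, and a last reported contact date on or after day 59. SAP 5.5.6 already uses that date for censoring. Any later visit or telephone contact should qualify.
2. State in advance that event-free subjects without such contact are excluded, the same handling as for those without imaging, and add a sensitivity analysis that counts them as failures. The sentence should also say how a death adjudicated as not lesion-related before day 59 is classed, since that subject has no later contact but is not lost.
3. Add one supportive row with the same exact lower bound for events from enrollment through day 30. It must include Phase 1 and day 0; the day 1-30 adverse-event window taken literally would drop both. The day-59 test remains the only formal test, and the row carries no decision.

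The cost is a few sentences and two output rows. A few late-enrolled or early-exiting subjects may need one documented later contact or will drop from the denominator.
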